3.8 Clinical Data with 3BNC117-LS and 10-1074-LS

Safety summary:

In comparison to a single infusion of either 3BNC117 or 10-1074, viremic individuals receiving one or three infusions of the combination of both antibodies showed significantly prolonged viral suppression. Rebound viremia was associated with the appearance of viruses that were resistant to 10-1074 in 3 of the 4 antibody-sensitive participants, but remained sensitive to 3BNC117. This is again consistent with the relatively shorter half-life of 3BNC117, which led to a period of 10-1074 monotherapy at the end of the observation period. The participant with the lowest initial viral load only returned to baseline viremia after both antibodies were below the limit of detection, and rebound viruses remained sensitive to both antibodies. Overall none of the 4 participants that were initially sensitive to the two antibodies developed *de novo* resistance to 3BNC117, despite the residual viremia observed in three of these participants and frequent

3BNC117-LS and 10-1074-LS are being evaluated in two ongoing first-in-human (FIH) phase 1 studies (NCT03254277, NCT03554408). Twenty-seven participants (6 HIV-infected individuals on suppressive ART) received 10-1074-LS at doses ranging from 150 mg or 300 mg SC up to 30 mg/kg IV, and 39 (15 HIV-infected individuals on suppressive ART) received 3BNC117-LS at the same dose levels. The admixture of the two antibodies has also been administered subcutaneously to 18 HIV-uninfected participants so far. Both intravenous infusions and subcutaneous injections have been well tolerated without Grade 3 adverse events or serious adverse events deemed possibly related to the antibodies reported to date. The safety profiles of the LS-variants so far are similar to the parental antibodies.

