Single infusions of 3BNC117 and 10-1074, dosed at 30 mg/kg, led to an average decline in viremia of $1.48 \log_{10}$ copies/ml (range = 0.8-2.5 and SD = $0.6 \log_{10}$ copies/ml) (Caskey, Klein et al. 2015) and $1.52 \log_{10}$ copies/ml (range = 0.9-2.06 and SD = $0.4 \log_{10}$ copies/ml) (Caskey, Schoofs et al. 2017). The average decline in viral load for 4 viremic participants who received one or three infusions of the 3BNC117 and 10-1074 combination was $2.05 \log_{10}$ copies/ml (range = 1.58-2.57 and SD = $0.7 \log_{10}$ copies/ml) (Bar-On et al. 2018).

A recent study, ACTG NWCS 413, utilized the Monogram PhenoSense assay to estimate baseline 3BNC117 and 10-1074 sensitivity of HIV pseudovirions that express envelope proteins representative of the quasispecies of proviral HIV-1 DNA in PBMCs. For 3BNC117, the median IC₅₀ was $0.087 \mu\text{g}/\text{mL}$ (Q1, Q3 of 0.061, 0.183) and median IC₈₀ was $0.301 \mu\text{g}/\text{mL}$ (Q1, Q3 of 0.206, 0.680); whereas for 10-1074, the median IC₅₀ was $0.044 \mu\text{g}/\text{mL}$ (Q1, Q3 of 0.020, 0.222) and median IC₈₀ was $0.184 \mu\text{g}/\text{mL}$ (Q1, Q3 of 0.066, 1.578). 61% (37/61) of the participants' virus swarms fell under the predicted sensitivity threshold of IC₈₀ < $1 \mu\text{g}/\text{mL}$ to both 3BNC117 and 10-1074, with 77% and 74% falling under this level for 3BNC117 only and 10-1074 only, respectively, and 89% for either antibody.

Table 4 shows the minimum average decline in plasma HIV-1 RNA levels (\log_{10} copies/ml) that can be detected with 80% power and a two-sided 0.05 test, assuming a standard deviation of 0.7 (\log_{10} copies/ml) from the 3BNC117 plus 10-1074 data. If 4 out of 10 participants harbor viruses sensitive to both antibodies, the minimum average decline in plasma HIV-1 RNA levels that can be detected with 80% power and a two-sided 0.05 test is $1.49 \log_{10}$ copies/ml. If we assume 60% of the participants will be sensitive to either antibody, the probability of observing at least 4 responders (HIV-1 RNA $\geq 0.5 \log_{10}$ copies/ml) out of up to 10 enrolled participants who receive 3BNC117-LS and 10-1074-LS is 0.95.

Table 4. Minimum average decline in plasma viremia that can be detected for varying sample sizes

N	SD (\log_{10} copies/ml)	two-sided test alpha =0.05	
		Minimum average decline in plasma HIV-1 RNA (\log_{10} copies/ml)	Effect size
3	0.7	2.29	3.26
4	0.7	1.49	2.13
5	0.7	1.18	1.68
6	0.7	1.00	1.43
7	0.7	0.89	1.27
8	0.7	0.81	1.16
9	0.7	0.75	1.07

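### The planning SD of 0.7 behind Table 4 cannot be the SD of the four participants it is credited to: with n = 4 and range 1.58–2.57, the SD cannot exceed 0.58

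*Combined protocol and SAP*

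**What the plan says.** Section 8.2 (Antiviral activity) summarises earlier experience with the parental antibodies. For the combination it reports "The average decline in viral load for 4 viremic participants who received one or three infusions". The mean it gives for these four is 2.05 log10 copies/ml, and the spread is reported as "range = 1.58-2.57 and SD" of 0.7.

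Table 4 then lists the smallest mean decline detectable at each N from 3 to 10, "with 80% power and a two-sided 0.05 test, assuming a standard deviation of 0.7" log10 copies/ml. The text says this SD comes "from the 3BNC117 plus 10-1074 data". The stated values run from 2.29 at N = 3, through 1.49 at N = 4 and 1.18 at N = 5, to 0.70 at N = 10.

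The text applies one row in words. If 4 of 10 participants carry virus sensitive to both antibodies, the detectable decline is given as 1.49. The other rows have no population label.

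Sections 5.1 and 5.2 do not make antibody sensitivity a condition of entry. Section 3.12 defines the viral load outcome for viremic participants without restricting it to sensitive ones.

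**The concern.** The range is too narrow for the SD. The four values span 2.57 − 1.58 = 0.99, and an SD of 0.7 from four observations needs a wider spread. The sentence that supplies the planning SD therefore contradicts itself.

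This matters beyond a typing slip because 0.7 is the declared input to Table 4, and Table 4 is the only power statement for the antiviral part of the primary outcome. An error in the SD passes in proportion into all eight rows and into the 1.49 sentence. As written, a reader would take 0.7 to be an observed SD.

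**Working it through.** **Inputs, all from Section 8.2.** n = 4; mean 2.05; range 1.58 to 2.57; SD 0.7; 80% power; two-sided alpha 0.05.

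**1. Reproduce Table 4.** I used a one-sample two-sided t-test on change from baseline with exact noncentral-t power. Detectable decline = effect size × SD.

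| N | Effect size at 80% power | × 0.7 | Table 4 |
|---|---|---|---|
| 3 | 3.264 | 2.285 | 2.29 |
| 4 | 2.128 | 1.490 | 1.49 |
| 5 | 1.682 | 1.177 | 1.18 |
| 6 | 1.435 | 1.004 | 1.00 |
| 7 | 1.273 | 0.891 | 0.89 |
| 8 | 1.156 | 0.809 | 0.81 |
| 9 | 1.067 | 0.747 | 0.75 |
| 10 | 0.996 | 0.697 | 0.70 |

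Every row agrees. The calculation is sound given its input.

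**2. Largest SD that n and the range allow.** For n = 4 the sample SD is greatest with two values at each end: SD = R × √(n / (4(n − 1))) = 0.99 × √(4/12) = 0.572. If the endpoints were rounded from 1.575 and 2.575, it is 1.00 × √(1/3) = 0.577. The stated 0.7 exceeds both.

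**3. Add the stated mean.** The four values sum to 4 × 2.05 = 8.20. The extremes take 1.58 + 2.57 = 4.15, so the other two sum to 4.05.
- Smallest SD, both at 2.025: √[(0.47² + 0.52² + 2 × 0.025²)/3] = 0.405.
- Largest SD, at 1.58 and 2.47: √[(2 × 0.47² + 0.52² + 0.42²)/3] = 0.544.
- If the mean is really 2.055, the upper value becomes 0.549; with rounded endpoints as well, 0.555.

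So the SD consistent with the sentence is about 0.41 to 0.55.

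**4. Effect on the N = 4 row, if n and the range are right.** Effect size 2.128.
- SD 0.405: 0.86
- SD 0.549: 1.17 (SD 0.555: 1.18)
- SD at the cap, 0.572 to 0.577: 1.22 to 1.23

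The plan states 1.49. Even at the cap it is too large by a factor of 0.7/0.577 = 1.21.

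**5. All enrolled participants, as an illustration only.** The documents give no mean decline for participants not sensitive to both antibodies, so the following are assumptions. Take 61% dual-sensitive (the Section 8.2 share for IC80 below 1 µg/ml) with mean 2.05 and SD 0.5, and the other 39% with mean m.
- m = 1.5, SD 0.5: variance 0.25 + 0.61 × 0.39 × 0.55² = 0.322, SD 0.57. Detectable at N = 10: 0.57.
- m = 0, no spread: variance 0.61 × 0.25 + 0.61 × 0.39 × 2.05² = 1.152, SD 1.07. Detectable at N = 10: 1.07.

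The table's 0.70 lies inside this interval. With SD 0.5 in both groups, the mixture SD equals about 0.7 when m is about 1.05.

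**The case against.** **Table 4 is correct for the assumption it declares.** This stands. The fault is in the input and its attribution.

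**The documents do not show which figure is wrong.** This also stands. The SD of the two endpoints alone is 0.99/√2 = 0.700, which is one conceivable origin of the figure, but nothing in the text confirms it. The number of participants or the range could equally be the misprint.

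**A planning SD of 0.7 is prudent.** This stands in part. An SD of 0.5 from four people has a 95% interval of roughly 0.28 to 1.86 under normality, so 0.7 is a reasonable conservative choice. The plan, however, presents it as what was observed.

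**Little depends on it.** Largely right. Section 8.1 calls the analysis primarily descriptive and any inference hypothesis generating, names no test for viral load, and no decision rule uses Table 4. At the cited mean of 2.05, four participants give about 96% power even with SD 0.7.

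**A stronger reading that is not supported.** A reader might infer that the four were all dual-sensitive, that the N = 5 to 10 rows describe the mixed enrolled sample, and that Table 4 is therefore too optimistic for those rows. Section 3.8 does say "Overall none of the 4 participants that were initially sensitive to the two antibodies" developed new 3BNC117 resistance, and the match in number is suggestive. But Section 8.2 calls its four only viremic, so the link is an inference. The text applies the table only to the sensitive subset, and the upper rows can be read as 5 to 10 sensitive participants. The mixture SD in step 5 falls on either side of 0.7 depending on declines the documents do not report. The 61% also uses a different cut-off from this trial's own definition of sensitivity, IC50 below 0.25 µg/ml (Section 6.2.12).

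**Conclusion.** The internal inconsistency is certain and needs no outside source: n = 4, range 1.58–2.57 and SD 0.7 cannot all be true. The consequence for Table 4 is conditional.

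- If n and the range are right, the stated 1.49 for four dual-sensitive participants is too pessimistic; the figure is about 0.86 to 1.17, and at most 1.23. This also assumes that the four earlier participants are a fair guide to that subset.
- If 0.7 is right, Table 4 stands and the range or n must be corrected.

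No error is shown for the enrolled sample as a whole. What is missing there is a statement of whom N counts. The point is worth correcting because it concerns the only stated power for a primary outcome and is cheap to put right. It gives no reason to change the sample size.

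**What to change.** 1. Check n, range and SD for the combination data against the source and correct whichever is wrong.
2. Recompute Table 4 and the 1.49 sentence with the reconciled SD. Alternatively, keep 0.7 and describe it as a conservative planning assumption, not as the observed SD.
3. State whether N in Table 4 counts participants sensitive to both antibodies or all enrolled participants.
4. Optionally, because entry does not require sensitivity, add rows for all enrolled participants over a stated range of mixture SDs. Under the step 5 assumptions that is about 0.57 to 1.07, giving about 0.57 to 1.07 at N = 10 against the present 0.70. Label these rows as dependent on assumptions.

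Cost: one table and one sentence to recompute, plus a label. Design, conduct and sample size are unaffected.

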4 STUDY DESIGN

The proposed study is a phase 1, open label, single arm study to evaluate the safety, pharmacokinetics and antiviral activity of single intravenous infusions of 3BNC117-LS and 10-1074-LS in viremic HIV-infected individuals. (Figure 4, Study Design).

Figure 4: Study Design

Ten eligible participants will be enrolled sequentially in the study and will receive each mAb, dosed at 30 mg/kg intravenously and in sequence on study day 0. Following mAb administration, study participants will return for safety assessments on days 1 and 3, and weeks 1, 2, 3 and 4 following dosing, then bi-weekly or monthly until the end of study follow up as indicated in the Time of Events Schedule (**Appendix A**). All participants will be followed for 24 weeks after 3BNC117-LS and 10-1074-LS administration.

Safety assessments will be performed at multiple time points following 3BNC117-LS and 10-1074-LS infusions. Serum samples for PK measurements will be collected before and at the end each mAb infusion administration and at multiple subsequent time points during study follow up, as indicated in the Time of Events Schedule (**Appendix A**). Samples will also be collected for measurement of HIV-1 plasma RNA levels before 3BNC117-LS and 10-1074-LS infusions (screen and day 0) and at every follow up visit. T cell subsets will also be monitored during study follow up. Assessments will also include measurement of ADA responses and sequencing of plasma envelope before infusions and after viral rebound (first time point after viremia nadir is reached and VL is $> 1,000$ copies/ml).

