8.2 Sample Size Considerations

Five to 10 evaluable participants are sought. The total number of screened participants to achieve 5 to 10 evaluable participants is estimated to be 15 to 30. Replacement for 2 participants lost to follow up prior to week 4 will be allowed.

Safety:

We expect that the administration of a single infusion of 3BNC117-LS in combination with 10-1074-LS will be generally safe and well tolerated.

The sample size of 5 to 10 participants receiving 3BNC117-LS and 10-1074-LS in combination will provide 95% probability of observing a treatment-related AE that would occur in 26% to 45% or more of treated participants. If none of the participants experiences a grade 3 AE related to 3BNC117-LS and/or 10-1074-LS, the one-sided 95% upper confidence bound for the rate of AEs in the population is 25.9% to 45.1%.

Pharmacokinetics:

Based on the pharmacokinetic profile of VRC01LS in humans, another anti-HIV-1 antibody targeting the same gp120 site as 3BNC117-LS, 3BNC117-LS and 10-1074-LS data in NHP, and preliminary 3BNC117-LS and 10-1074-LS data in humans, it is expected that the half-lives of 3BNC117-LS and 10-1074-LS will be approximately 3-fold higher than the unmodified antibodies. Therefore, we expect that 3BNC117-LS will have a $t_{1/2}$ in humans of approximately 70 days. Similarly, we expect that 10-1074-LS will have a $t_{1/2}$ in humans of approximately 90 days.

In a previous study with 10-1074, the mean elimination half-life of approximately 24 days (SD 6.6 days) in HIV-uninfected and 12.8 days (SD 4.9 days) in viremic HIV-infected individuals (Caskey et al 2017). 3BNC117 has a mean elimination half-life of approximately 17.6 days (SD 5.7 days) in HIV-uninfected and 9.6 days in viremic HIV-infected individuals (SD 2.9 days) (Caskey et al., 2015). PK parameters were maintained when the two antibodies were administered in combination.

The margins of error at 95% confidence level for estimating the mean elimination half-life of either mAb, based on standard deviations in the range of 4.5 to 6.5 days using the available pharmacokinetics data of 3BNC117 and 10-1074, and 5 or 10 participants are included in **Table 3**.

Table 3. Margin of Error at 95% Confidence Level for Estimating the Mean Elimination Half-life of 3BNC117-LS and 10-1074-LS

Standard Deviation (days)	95% margin of error (+/- days) n = 5	95% margin of error (+/- days) for n = 10
4.5	3.9	2.8
5	4.4	3.1
5.5	4.8	3.4
6	5.3	3.7
6.5	5.7	4.0

Antiviral activity:

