8.4 Participant Enrollment and Follow-Up

The total number of evaluable participants in the study will be 5 to 10.

An over-enrollment of 2 participants will be allowed if participants drop-out prior to week 4. Participants who are discontinued from the study due to AEs will not be replaced. Additional participants will be enrolled after study withdrawal is confirmed. If a participant drops out after receiving 1 or both study drugs, he/she will be invited to return every 4 weeks, for at least 3 months after antibody infusion, for safety monitoring only.

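### The 0.95 chance of at least four responders in Section 8.2 holds only at N = 10 within the permitted 5 to 10 (0.34 at N = 5), and its 60% input carries the label of a rate cited as 89%

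*Combined protocol and SAP*

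**What the plan says.** The antiviral part of Section 8.2 first cites a study of baseline sensitivity by the PhenoSense assay. It reports that "61% (37/61) of the participants' virus swarms fell under the predicted sensitivity threshold" of IC80 below 1 µg/mL for both antibodies. The single-antibody rates are 77% (3BNC117) and 74% (10-1074), "respectively, and 89% for either antibody".

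The next paragraph gives the detectable decline if 4 of 10 participants have virus sensitive to both antibodies. It then states: "If we assume 60% of the participants will be sensitive to either antibody, the probability of observing at least 4 responders" (a responder being defined by 0.5 log10 copies/ml) "out of up to 10 enrolled participants who receive 3BNC117-LS and 10-1074-LS is 0.95".

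On sample size, Section 8.2 opens with "Five to 10 evaluable participants are sought". Section 8.4 says "The total number of evaluable participants in the study will be 5 to 10", and the Protocol Summary also gives 5 to 10. Section 4 differs: "Ten eligible participants will be enrolled sequentially in the study".

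Elsewhere in Section 8.2 both ends of the range are shown. The safety bounds are given as 25.9% to 45.1%, and Table 3 has a column for n = 5 and one for n = 10. The responder probability is a single value.

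**The concern.** The sentence reassures the reader that enough participants will respond for the antiviral outcome to be informative. Saying up to 10 makes 0.95 read as a property of the whole permitted range, although a binomial tail with a fixed threshold of four falls quickly as N falls. With five participants, four responders means 80% of them, against an assumed rate of 60%.

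The label compounds the problem. The same section puts sensitivity to either antibody at 89%, so a reader cannot tell whether 60% is the rate for both with the wrong word attached or a discounted rate for either. At N = 5 the choice matters: the answer is 0.34 at 60% and 0.90 at 89%.

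What is at stake is a stated design property, not an analysis result.

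**Working it through.** **Inputs, all from Section 8.2 unless noted**
- Assumed responder probability: p = 0.60, labelled as sensitivity to either antibody.
- Threshold: at least 4 responders.
- Stated result: 0.95 for up to 10 participants.
- Permitted evaluable N: 5 to 10 (Protocol Summary, Sections 8.2 and 8.4); ten in Section 4.
- Cited rates: both 37/61 = 0.607; 3BNC117 0.77; 10-1074 0.74; either 0.89.

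**Formula.** With X ~ Binomial(N, p), P(X ≥ 4) = 1 − Σ (k = 0 to 3) C(N, k) p^k (1 − p)^(N − k). This treats every sensitive participant as a responder and nobody else as one, as the plan's own figure implicitly does.

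**Step 1: reproduce the plan's figure (N = 10, p = 0.60)**
- k = 0: 0.4^10 = 0.0001
- k = 1: 10 × 0.6 × 0.4^9 = 0.0016
- k = 2: 45 × 0.36 × 0.4^8 = 0.0106
- k = 3: 120 × 0.216 × 0.4^7 = 0.0425
- The unrounded terms sum to 0.0548, so P(X ≥ 4) = 0.9452, which rounds to the stated 0.95.

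**Step 2: the lower end (N = 5, p = 0.60)**
- Exactly 4: 5 × 0.6^4 × 0.4 = 0.2592
- Exactly 5: 0.6^5 = 0.0778
- P(X ≥ 4) = 0.3370.

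**Step 3: the whole permitted range, under each reading of the input**

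| N | p = 0.60 (as assumed) | p = 37/61 (both) | p = 0.89 (either) |
|---|---|---|---|
| 5 | 0.3370 | 0.3484 | 0.9035 |
| 6 | 0.5443 | 0.5579 | 0.9794 |
| 7 | 0.7102 | 0.7228 | 0.9961 |
| 8 | 0.8263 | 0.8363 | 0.9993 |
| 9 | 0.9006 | 0.9078 | 0.9999 |
| 10 | 0.9452 | 0.9500 | >0.999 |

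**Step 4: which rate is 60%?** The cited rates fit together on the ordinary reading of both and either: 77 + 74 − 61 = 90%, one point from the 89% given for either. So 61% is the joint rate, and 60% lies next to it. The stated 0.95 agrees with p = 0.60 or 37/61 at N = 10; p = 0.89 would have given a value above 0.999.

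**Step 5: the sensitivity definition.** The 61% uses IC80 < 1 µg/mL. Sections 3.11 and 6.2.12 define sensitivity as IC50 < 0.25 µg/ml. Section 8.2 gives IC50 upper quartiles of 0.183 (3BNC117) and 0.222 (10-1074), so about 75% or more meet the IC50 cut-off for each antibody separately. The joint rate on that definition is not given. Assuming independence at 75% each, p = 0.75 × 0.75 = 0.56, and N = 10 gives 0.91. This illustrates the scale only; the documents do not supply the joint rate.

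**The case against.** The strongest reply is that nothing has been miscalculated and nothing depends on the number. A reader might take this for an arithmetic error, but Step 1 reproduces the figure. Section 8.1 calls the study exploratory, with inferences that are not confirmatory, and no decision rule uses four responders. All of this stands, and it limits the weight of the point.

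A second reply is that 60% is introduced as an assumption and may be deliberately conservative. Single infusions of either parental antibody gave mean declines near 1.5 log10, so virus sensitive to one antibody only could well respond, and *either* could be the intended population. That is possible, but the text does not say the 89% was discounted or why the result should land on the rate for both. If 89% were used, N = 5 would give 0.90 and the small-N problem would largely disappear. The 0.34 is therefore conditional on p = 0.60.

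Three stronger readings are tempting but not supported:
- **Enrollment could stop once results look good.** The documents do not say what decides between 5 and 10, but nothing ties enrollment to viral-load results.
- **With five enrolled, about three would be dual-sensitive, so the comparison is underpowered.** Section 8.1 plans no test in a sensitive subset, sensitivity is not an entry criterion, and Table 4 already discloses the N = 3 row (2.29 log10).
- **Ten is the settled target, so aligning to it costs nothing.** Only Section 4 says ten; the Protocol Summary and Sections 8.2 and 8.4 say 5 to 10.

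**Conclusion.** The point holds as a mislabelled input and a figure given only for the most favourable N. Within the permitted 5 to 10, the 0.95 is right at N = 10 alone; at p = 0.60 it falls to 0.90 at N = 9, 0.83 at N = 8 and 0.34 at N = 5. The 60% agrees with the cited rate for both antibodies (61%), not with the rate for either (89%).

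These values assume independent participants with a common responder probability, sensitivity equated with response, and p kept at 0.60. It is worth correcting because the sentence misstates a design property. It is not a threat to the trial's conclusions, which will rest on descriptive summaries.

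**What to change.** In Section 8.2:
- Change *either* to *both* in the responder sentence, or keep *either* and state why 60% was chosen below the cited 89%.
- Say that the 61% behind the assumption rests on IC80 < 1 µg/mL, which differs from the protocol's IC50 < 0.25 µg/ml definition. Recomputing p on the IC50 definition cannot be done from the figures in the document.
- Replace the single 0.95 with the two ends of the range, as is already done for safety and pharmacokinetics. Possible wording: assuming 60% of participants have virus sensitive to both antibodies and that each of them responds, the probability of at least four responders is 0.34 with 5 evaluable participants and 0.945 with 10.

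Across the document, reconcile the ten participants in Section 4 with 5 to 10 in the Protocol Summary and Sections 8.2 and 8.4. Which number is intended is for the sponsor to say.

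The changes to Section 8.2 are rewording only. Their downside is a less favourable stated probability below N = 10. Reconciling on 5 to 10 is also rewording; fixing the target at ten would double the permitted minimum and carries an accrual cost.
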